1.0 INTRODUCTION

1.1 Abstract

The primary purpose of this study is to determine if by offering a vapocoolant (cold spray) to Nuclear Medicine outpatients prior to having an intravenous catheter (IV) inserted will increase patient satisfaction of IV insertion as well as determine if pain of insertion is decreased. Furthermore, this study will examine the patients’ willingness to use a vapocoolant spray with future IV insertions and potentially reduce anxiety when an IV insertion is required.

1.2 Relevant Literature and Data Rationale

Patients requiring intravenous (IV) access are faced with the necessity of an invasive and uncomfortable procedure. Approximately 25 million people in the United States and 90% of all hospitalized patients require IV catheter insertion. (Levitt, F.C. & Ziemba-Davis, M., 2013).

Pain management during medical care, in addition to being recognized as a basic human right, impacts a patient’s satisfaction. (Hogan, M., Smart, S., Shah, V., & Taddio, A., 2014). The Joint Commission standards endorsed by the American Pain Society require health care providers to assess and manage pain. The standard of care for managing pain associated with invasive procedures is to anticipate and ameliorate pain to the greatest degree possible. (Levitt et al., 2013).

Research studies have been conducted to determine the least painful method of anesthetizing a peripheral IV site in addition to studying patient’s perception of the anesthetizing agent. One study found that the use of 1% lidocaine intradermally before insertion of IV catheter was the most effective technique in reducing IV catheter insertion discomfort (Winfield, C., Knicely, C., Jensen, C., Taylor, S., Thomas, K., Burns, S., & Quatrara, B., 2013) however this particular method requires a physician order for lidocaine injection, can become costly and subjects the patient to an additional needle stick. The advantage of utilizing a vapocoolant spray has been researched and found to likely reduce pain during intravenous cannulation and are not likely to make cannulation more difficult nor cause serious adverse events. (Griffith, R., Jordon, V., Herd, D., Reed, P., & Dalziel, S., 2016).

This study is necessary to further support the use of a vapocoolant spray as a tool in managing pain or the perception of pain prior to IV cannulation insertion.

2.0 STUDY OBJECTIVES

2.1 Primary Objective

The Nuclear Medicine department at Aultman Hospital seeks to address the issue surrounding pain and satisfaction associated with the invasive procedure of starting an intravenous catheter (IV) for the injection of radiopharmaceutical

and/or medications needed to complete nuclear images and provide for viable scans. The primary purpose of this study is to determine if by applying a vapocoolant (cold spray) at the IV insertion site on Nuclear Medicine outpatients will increase the satisfaction with IV insertion as well as determine if pain of insertion is decreased. Furthermore, this study will examine the patients' perception in using a vapocoolant spray as a way to improve upon the traditional method of starting IV's that do not offer pain management prior to their insertion. A sterile water mist will be used as the comparator spray to add validity to the standard of care arm.

Research Questions:

For the purpose of this study, the following questions will be addressed:

1. Will patients perceive a vapocoolant spray to be more effective in reducing pain prior to IV cannulation insertion over saline spray?
2. Will the use of a vapocoolant spray increase satisfaction with insertion at an intravenous site over that of a sterile water spray?

2.2 Secondary Objective

The broader implication to this study is to bring awareness to both caregivers and patients alike that there are options for pain management when IV insertions are needed and/or required. Furthermore, vapocoolant sprays are already being utilized for pain management in accessing port-a-cath sites in our Radiology department therefore this study could use the same spray as is indicated for its use in accessing IV insertion sites.

3.0 SUBJECT SELECTION

3.1 Inclusion Criteria

Patients who voluntarily agree to participate in the study and are scheduled for a Nuclear Medicine Stress Test at Aultman Heart Center.

3.2 Exclusion Criteria

Patients will be excluded from this study for the following reasons:

- 1) If this is the first time the patient has ever had an intravenous catheter (IV).
- 2) Any patient under the age of 18 and/or any patient over the age of 85.
- 3). Those who are or may be pregnant.
- 4) Any woman who is breastfeeding.
- 5) Any patient who has taken any narcotic, sedative, and/or as needed anti-anxiety medication within the last 8 hours of the intravenous catheter insertion.
- 6). Any persons who are non-English speaking.
- 7). Any persons who are decisionally impaired.

- 8). Any persons who are illiterate.
- 9). Any patient who has had a known hypersensitivity and/or allergy to Ethyl Chloride.
- 10). Any persons who have been diagnosed with Raynaud's Syndrome and/or Carpal Tunnel Syndrome.

4.0 SUBJECT ENROLLMENT

The study population for this research is a convenience sample of patients who have been ordered to undergo a Nuclear Medicine Stress Test at Aultman Hospital Heart Center. Upon arrival to the Nuclear Medicine department the patient must check in at the front desk for his/her scheduled exam. The patient will need to fill out the necessary documents required by the nuclear medicine department to perform the stress test imaging. In addition to the patient will be given a letter to make them aware that a research study is being conducted within the department. (See Attachment 1-Explanation of Research Study). This letter is only intended to inform the patient that a research study is being conducted this is not intended to be used for the consent process. When it is time for the patient's exam the researcher will take the patient back to the injection room where an explanation for the exam and need for IV access will be explained.

The researcher of the study will have information from the patient's health record that will indicate a patient's age and gender. The researcher will automatically exclude any persons who do not meet the age requirement in addition to asking the patient if this is the first time they have ever had an intravenous catheter placed. Also at this time the researcher will determine if the patient is able to speak and read English as well as determine if the patient is decisionally aware. The patient will be asked additional questions to determine the patient's inclusion/exclusions to participate in the research study. (See Attachment 2- Inclusion/Exclusion Criteria Checklist). If the patient does not meet the criteria set forth for the study the patient will be told that they do not qualify at that time and that their nuclear exam will continue as ordered without the use of the research interventional spray being used in the study and they will get an IV using the method currently in practice. If a patient is eligible to participate in the study the researcher will make the patient aware of their eligibility and again explain the use of a vapocoolant spray vs. a placebo spray prior to IV insertion. The researcher will explain to the patient why the study is being conducted and allow the patient adequate time to decide on whether to participate in the study. If the patient chooses to participate in the study they will be asked to read and sign/date the HRRB approved research consent form. (See Attachment 3- Consent Form). Subjects will be given ample time to consider participation and have all of their questions addressed.

5.0 STUDY DESIGN AND PROCEDURES

5.1 Design/Study Type

This is a single blind interventional study with a post design using a convenience sample of patients undergoing a Nuclear Medicine Stress Test at Aultman Heart Center.

5.2 Selection of Instruments

A questionnaire will be filled out by the researcher while asking the patient questions prior to and after IV insertion. (See Attachment 4- Patient Questionnaire and Researcher Documentation Form). The patient will be provided with a visual diagram of a 0-10 pain scale and a 1-5 satisfaction Likert Scale. (See Attachment 5- Visual Pain and Satisfaction Scale).

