5.3.2 Product Handling and Storage

The manufacturer of Nature's Tears Eye Mist MDS report (see Attachment 7) indicates that the can should be stored at room temperature and should not be stored at temperature's greater than 50°C (120°F). (Biologic Aqua Technologies, 2013). For the purpose of this study the Nature's Tear Mist spray will be refrigerated to "mimic" a cold spray. There are no documented contraindications that refrigeration would affect the sterility or application of the spray. The refrigerator is located in the Nuclear Medicine department's "Hot Lab" that is monitored by temperature control and is in a locked room. The Gebauer Company's Safety Data Sheet (SDS) (see Attachment 6) indicates that the ethyl chloride spray should be stored in cool, dry well ventilated area. Protect against physical damage. Do not subject to temperatures above 120°F (50°C). Do not store near high frequency ultrasound equipment or non-explosion proof electrical equipment. (Gebauer Company, 2013.) This product will be stored in a locked cabinet located in the Nuclear Medicine Department's scan room which is temperature controlled at 72°F.

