5.3.3 Intervention Administration

The researcher will access a peripheral IV site using the hospital protocol on inserting IV catheters. The researcher will select an IV site; the patient's skin will be cleansed prior to the intervention spray being applied per hospital protocol. The researcher will then spray the intervention spray made by the Gebauer Company according to the manufacturer's recommendations which is to spray the Ethyl Chloride aerosol can for 4 to 10 seconds from a distance of 3 to 9 inches (8-23 cm). Do not spray longer than 10 seconds. Spray the area for the time recommended or until the skin just turns white; do not frost the skin. With skin, taut, quickly introduce the needle because the numbing effect of ethyl chloride only lasts for a few seconds to a minute. (Gebauer's Ethyl Chloride Spray, 2016). Reapplication of the spray to the area when it has been too long or is no longer "numb" is also indicated by the manufacturer but for the purpose of this study the patient will only have the application applied once. For the control group the patient's skin will be prepared per hospital protocol then the researcher will apply the Nature's Tears Eye Mist to the area for 4-10 seconds prior to IV access.

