5.4 Data Collection

The questionnaire (See Attachment 4- Patient Questionnaire and Researcher Documentation Form) will include the following questions prior to the use of the intervention:

- 1.) Using the visual analog scale provided how would you rate your pain the last time you remember having an IV inserted?
- 2.) Using a 0-5 Likert scale please rate how satisfied you were the last time you remember having an IV inserted?
- 3.) Do you think it is important to control the pain of starting an IV?

Once the IV has been placed the researcher will ask the patient the following questions:

- 1.) Using the same 0-10 pain scale how would you rate this IV insertion?
- 2.) Using the same 1-5 satisfaction scale how satisfied were you with this IV insertion?
- 3.) Would you choose to have a spray used again if you needed to have an IV inserted in the future?

The researcher will document the patient responses as well as the angiocatheter size, angiocatheter location, numbers of IV start attempts, the time that the intervention was applied and what interventional spray was used. (See Attachment 4- Patient Questionnaire and Researcher Documentation Form). This information will be coded and will be used to analyze study results post intervention. The presence of adverse events will be monitored and documented for 120 minutes following the IV insertion.

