6.0 STUDY ADMINISTRATION

6.1 Description of Study Process

This study will be conducted using patients who are ordered to undergo a Nuclear Medicine Stress Test. These patients will only be seen in this department the day that the stress test exam is performed. The anticipated time it will take to gather the patient's information, conduct the recruitment and consent portion of the study is approximately 30 minutes per patient. This study will use a convenience sample of patients over a 4-month period. The target goal is 30 patients; however, researchers may recruit up to 80 patients.

Once the determination has been made by the researcher that the patient is a candidate for the study the patient has consented they will be assigned to either the control group or experimental group through a computerized randomization sheet. Both the control group and experimental group will be equally represented. Once the IV has been placed regardless of what intervention was used the patient will then be asked by the researcher the questions as stated above.

The participants will only have the intervention used on a first attempt IV access. If the participant has to have additional attempts by the researcher to start an IV, their study will automatically be excluded.

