6.2 Data Quality and Confidentiality

The information obtained during this study will remain confidential and will be stored in a file cabinet with a key lock. [name] and [name] the Sub- investigators of this study under the supervision of the Principle Investigator [name] will be responsible for the following:

- 1). Explaining the study to potential participants along with conducting the consent process with the patient.
- 2). Asking related questions to consented participants regarding the research information obtained during the conduction of this study.
- 3). The medical review of patient health information determine eligibility.
- 4). Administration of the vapocoolant spray and placebo spray prior to IV access.
- 5). Performing IV access on study participants
- 6). Identifying any adverse reaction to the intervention being used. All adverse events will be reported to and managed by the Principle Investigator.

These responsibilities performed only by the Sub Investigators will ensure that there will be no threat to the validity of the study being performed and its study results. Data for this study will be kept only as long as the study is being conducted and analyzed for results. Once this information has been obtained all records will be discarded in accordance with hospital policy and applicable regulations. Within the consenting process the patient will be made aware that their information will be kept confidential and that the patient has the right to end their participation in the study at any point.

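### An unblinded researcher sprays, inserts the IV, then asks for and records both subjective outcomes; patients could mark the scales themselves

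*Combined protocol and SAP*

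**What the plan says.** All references are to the combined protocol and SAP.

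- **Blinding.** Section 5.1: "This is a single blind interventional study with a post design". Section 5.3.1 says that patients will not be able to identify the sprays. It says nothing about masking the researcher.
- **Spraying and insertion.** Section 5.3.3 gives both to the researcher. For the active arm, "The researcher will then spray the intervention spray made by the Gebauer Company"; for the control arm, the researcher applies the water mist. The researcher also selects the site and places the catheter.
- **Asking.** Section 6.1: once the IV is in, "the patient will then be asked by the researcher the questions as stated above". Section 5.4 lists these questions: pain on 0-10, satisfaction on 1-5, and willingness to have a spray again.
- **Recording.** Section 5.2: "A questionnaire will be filled out by the researcher while asking the patient questions prior to and after IV insertion". Under section 5.4 the researcher also records "the time that the intervention was applied and what interventional spray was used".
- **The plan's own assessment.** Section 6.2 lists consent, eligibility review, spraying, IV access, questioning and adverse-event identification as duties of the two sub-investigators. It concludes: "These responsibilities performed only by the Sub Investigators will ensure that there will be no threat to the validity of the study being performed".
- **Safeguards.** Patients are shown both scales (section 5.2). The placebo "spray will be refrigerated to" imitate a cold spray (section 5.3.2). The pre-procedure rating is the planned covariate (section 8.0).

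**The concern.** Pain and satisfaction have no objective referent, and the abstract and section 2.1 make them the primary purpose. Both are spoken aloud to the person who has just put the needle in. The satisfaction item is partly a verdict on that person's work, so a candid low score is hard to give. If the interviewer also knows the spray, the prompting, the tone and the reading of a hesitant answer can differ by arm, and the likely direction favours the vapocoolant.

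Two features of the plan do not help. Adjusting for the pre-procedure rating cannot remove a shift that enters only in the post-insertion rating. Recruiting up to 80 patients instead of 30 narrows the standard error around a biased difference, so a purely reporting-driven difference becomes more likely to be declared an effect.

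There is a smaller gap in the order of steps. Section 5.4 says that the questionnaire "will include the following questions prior to the use of the intervention", and section 5.3.3 puts site selection before spraying. Neither says whether the baseline answers, or the choice of vein and catheter, come before the researcher knows the assignment.

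**Working it through.** **Step 1. Does the person who collects the outcomes know the assignment?** The plan does not say so in one sentence, but four points lead to it:

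1. The design is single blind (5.1), and only patients are said to be unable to identify the sprays (5.3.1).
2. The products are kept in different places: a refrigerator in the Hot Lab and a cabinet in the scan room (5.3.2).
3. Their application instructions differ; the active spray has a distance range and a skin-whitening end point (5.3.3).
4. The researcher writes down which spray was used (5.4).

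Sections 5.2, 5.4 and 6.1 give the post-insertion questions and the form to the researcher. Section 6.2 gives spraying, insertion and questioning to the same small team, with no requirement to separate them. The visible text describes no masked assessor, self-completion or neutral script.

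**Step 2. How much could a reporting shift matter?** The plan has no figure to reproduce here, so this is an illustration.

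Inputs from the plan: N = 30 to 80 (6.1, 8.0) and equal arms (6.1).

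Assumed inputs:
- no true effect
- a reporting shift b on the 0-10 pain scale
- SD of 2 or 2.5
- pre-post correlation r of 0 to 0.5
- two-sided testing at 0.05; section 8.0 prints 0.5, so the 5% benchmark is an assumption too

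*Unadjusted t-test:* SE = SD × √(4/N), df = N − 2, noncentrality = b/SE. The result is the probability that |t| exceeds its 0.05 critical value.

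Example with b = 0.5 and SD = 2:
- N = 30: SE = 2 × √(4/30) = 0.730; noncentrality 0.5/0.730 = 0.685; probability 0.101.
- N = 80: SE = 2 × √(4/80) = 0.447; noncentrality 0.5/0.447 = 1.118; probability 0.197.

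*Covariate-adjusted:* SE = SD × √(1 − r²) × √(4/N) × √(1 + 1/(N − 4)), df = N − 3.

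Example with b = 0.5, SD = 2, r = 0.5, N = 80: SE = 2 × 0.866 × 0.2236 × 1.0066 = 0.390; noncentrality 0.5/0.390 = 1.283; probability 0.245.

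Probability of a significant result with no true effect (nominal 5%), as ranges over SD 2-2.5 and, where adjusted, r 0-0.5:

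| Shift b | Analysis | N = 30 | N = 80 |
|---|---|---|---|
| 0.25 | adjusted | 5.8-6.6% | 7.2-9.7% |
| 0.5 | unadjusted | 8.3-10.1% | 14.3-19.7% |
| 0.5 | adjusted | 8.1-11.6% | 14.2-24.5% |
| 1.0 | unadjusted | 18.5-26.2% | 42.4-59.8% |
| 1.0 | adjusted | 17.9-32.2% | 41.9-71.7% |

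A simulation of the adjusted b = 0.5 cells (40,000 trials each) gave 8.2-11.6% at N = 30 and 14.2-24.3% at N = 80. With b = 0 it gave 4.8-5.3%, as it should.

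In every row the excess over 5% is larger at N = 80 than at N = 30. When r is well above zero, adjustment raises the false-positive rate, because it sharpens the comparison without touching the shift. The figures do not carry over to the 1-5 satisfaction scale, and none is given for it.

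**Step 3. Is self-marking feasible?** Patients already see both scales (5.2). Illiterate and non-English-speaking patients are excluded (3.2), and ability to read English is checked at screening (section 4.0). The material and the population both allow it.

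**The case against.** The strongest reply is that the rater is the patient, who is meant to be blind, looks at a printed scale and receives a chilled placebo. The researcher transcribes a number and does not judge one, and single blinding is openly declared. That stands as a limit on the size of the problem: patient expectation is partly controlled, and what remains is prompting, tone and interpretation. It does not remove the researcher's knowledge. The proposal also leaves the single-blind operator in place.

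Other points have some force:

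- Two sub-investigators share the duties, so one person doing every step for a given patient is an inference. The text says the researcher throughout, however, and requires no separation.
- The sentence in section 6.2 covers all six duties and may mean only consistency from a small team. Consistency is a fair aim, but the sentence as written denies any threat to validity.
- The contents of Attachments 4 and 5 are not in the text reviewed. Fixed question wording there would help, but the interviewer would still know the assignment.
- The illustration depends on the assumed shift. At 0.25 points the inflation is modest, and at 0.1 points it is almost nil (about 5.1-5.7%).
- Self-marking can leave blanks. With 15 patients per arm, one blank is 1/15, about 7% of that arm.

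**Conclusion.** The concern holds. As written, both main outcomes are elicited and recorded by an unblinded operator, and section 6.2 claims the opposite of what this arrangement does. Who does what is well supported by the text; that the researcher knows the assignment is an inference, but a firm one.

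The size of any bias is unknown. Under the assumptions above, a half-point shift in reported pain would roughly double the 5% error rate at 30 patients and multiply it by about three to five at 80. A much smaller shift would do little. This is a weakness in a declared single-blind design rather than a fatal flaw. It should be corrected because the correction is simple and protects the primary comparison.

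**What to change.** 1. **Self-marking.** The patient marks the post-insertion pain, satisfaction and future-use items on paper, out of the researcher's view. The sheet carries only the study number and a printed instruction to answer every item. The patient seals it in an envelope that is opened only at data entry.
2. **Order of steps.** State that the pre-procedure questions are answered, and the vein site and catheter size chosen and written down, before the assignment is revealed. This is a secondary tidy-up.
3. **Section 6.2.** Replace the sentence on validity with something like: *The sub-investigators who apply the spray and insert the IV know the assignment; patients therefore mark the post-insertion ratings themselves, out of the researcher's view.*
4. **Missing items.** Report blanks by arm, and do not hand sheets back for completion.

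The cost is a one-page form, envelopes and one line on sequence, with no extra staff. The downsides are an occasional missing item and a mode of collection that differs between the interviewer-recorded covariate and the self-marked outcome. Self-marking removes interviewer and recording effects. It does not remove cues given while spraying or inserting, or differences in sensation or skin appearance between the sprays, so the report should still describe the operator as unblinded.
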